## REMOTE (phone) COHORT

1. Subjects are contacted by the KPWA survey research team and provide oral consent over the phone in the initial screening and eligibility process; if eligible and interested, will be notified to expect a call from a research specialist to schedule their baseline phone visit. Survey research team mails consent form and welcome letter.
2. About 1 week after survey has mailed consent, and up to two weeks before the baseline phone visit, the research specialist (after confirming that the participant has the consent form in front of them) will review over the phone with the subject the written informed consent form (see attached) and describe the study to them, answer any questions, and obtain either written or online consent. If the participant is willing to consent online, after discussing the consent process and reviewing the consent materials, the RS will email a link to a REDCap form (see email script) with an online consent for the participant to electronically sign. If in written form, the participant will mail the form back to KPWHRI and a copy will be made and sent back out to the participant ideally within 2 weeks of receipt. The RS will also ask the subject to summarize the study to the best of their ability. If they are unable to do so or cannot recall the primary parts of the study (ex: that they have to wear a device periodically; that they will have coaching calls; that they will

be randomly assigned to one of two groups), they will be thanked for their time and excused from the study prior to randomization. During this phone call, the RS will also collect height and weight to ensure we send them the right size cuff along with their blood pressure monitor to ensure accuracy.

3. The research specialist will prepare and mail a packet to the potential participant including an activPAL device along with instructions on how to wear it for one week. The research specialist will order a scale (and measuring tape) to be sent to the participant as well as a blood pressure monitor. Instructions will be included. Envelopes for returning the activPAL device are also included.
4. Subjects will participate in a baseline phone visit approximately 30 days after initial screening into the study by the survey research group and roughly 2 weeks after their phone consent.
  - a. During the baseline phone visit, participants will either complete a survey containing self-reported scales regarding health symptoms (depressive symptoms, pain, fatigue), daily activities, and psychosocial mediators (e.g. habit strength, self-efficacy) with the research specialist or will complete the survey online (their preference). Participants will be guided through collecting their waist measurement, weight and blood pressure using the devices and tools sent ahead of time. Per instructions and reminders sent to participants, if they have consumed any caffeine or tobacco, or exercised within 30 minutes of the visit, the visit will be rescheduled. Participants will also be guided through the modified chair sit over the phone. All participants will be mailed a \$30 cash incentive for completing measurements at the baseline visit. If participants inquire about their blood pressure readings, we will advise them to see their provider if they have questions or concerns.
  - b. After baseline activPALs are received by mail, coaches will download the data and participants will be randomized (using a link created by the study biostatistician and programmer) to receive i-STAND (N = 142) or healthy lifestyle control (N = 142). To ensure that baseline sitting time is balanced, we will stratify participants into two groups based on self-reported sitting-time using median sitting time from our pilot work as a cut point: moderate (<8.5 hours/day) and high ( $\geq 8.5$  hours/day). We will also stratify by obesity level (30-35 vs 35+kg/m^2) and blood pressure (systolic BP over or under 130). Coaches will call participants to notify them of their assigned cohort and to schedule their baseline coaching visit. At this time they will also confirm if they prefer to use email or regular mail.
  - c. Participants who were randomized to i\_STAND and did not give us their email, will have their first feedback chart mailed to them, along with instructions (see attached) on how to retrieve encrypted emails in the future, in case they prefer to receive their feedback chart by email going forward. All other i-STAND participants who have given us permission to email, will have their charts sent via encrypted email as described in Supplement B. Because it does not require encryption, if the participant has expressed over the phone that they prefer to receive study materials by email, the i-STAND workbook will be sent by email at this time. If not, the notebook will be mailed by USPS. A fitness activity band will also be mailed from a third party vendor and a

standing desk. NOTE: We have amended Supplement B to request permission to send the activPAL feedback chart to i-STAND only participants (as an alternative option to sending them by mail).

- d. Within two weeks of completing the phone-based baseline measurements, participants randomized to receive the i-STAND intervention condition will have their first phone coaching session with their health coach. During the first intervention session they will review the feedback chart they were mailed which depicts their daily sitting time, standing time, and breaks from sitting from the activPAL they wore for baseline. In the case that the coach encounters difficulty with the STATA software that creates the feedback chart output, coaches will use the raw activPAL data (does not take sleep hours out of the download) and share this with participants. They will explain the data in the same way they would if they were able to produce a feedback chart. The health coach will provide background information on how sitting could impact their health. The coach will review the feedback chart with the participant, provide reinforcement for times during the week when the participant took more breaks from sitting, assess and enhance participant motivation and uncover values (using motivational interviewing principles) to inform developing an action plan to meet graded goals based on participant values. The action plan will include target goals, when/how/where tasks will be performed, strategies to overcome barriers, and how goals map to participant values. Discussion will cover principles of habit formation. The health coach will model taking breaks from sitting by inviting the participant to stand with them at least once during the phone session.
  - During the phone session, participants will be instructed in using the wrist-worn activity band and standing desk they were sent, to help remind them to take breaks from sitting. Our pilot work strongly supported the need for these cues. The band subtly vibrates to prompt a break at preselected intervals (ex: 15, 30 or 60 minutes) and will be set to prompt every 15 minutes to remind them regularly to take breaks from sitting. Because many older adults don't feel comfortable setting up technology and mobile tools, the device will be preset so it functions without syncing to another device. Participants who want to use the activity band smartphone application will receive additional instruction. Study staff will not have access to any data from the device. If any participants feel the frequency (every 15 minutes) is too much, study staff can re-set the band at a lower frequency based on the participants' preference.
  - Those who express interest in other features of the Fitness wrist band may receive a handout by email or mail showing how to program the device to track other things (ex: steps taken, calories burned), however the study does not track on any of these features/options and the coach will remind the participant that the study is solely interested in whether they find the vibration reminders useful as an outward reminder to stand. (*Usefulness will be measured in a 3-month survey (see section 3a next page).*
- e. Participants in the Healthy Lifestyle Control group will have their first phone-based coaching session where they will review the Healthy Living materials, go over in brief the first 5 topics, and advise the participant that after session 5, they can choose topics

of interest to focus on for the rest of the program. They will learn about how to set clear, actionable goals. As with the i-STAND group, if we have their email and their willingness to receive study materials by email, we will email them the Healthy Living workbook. Otherwise this will be sent by mail prior to the first call. The health coach will provide background information and help the participant choose topics of focus to inform developing an action plan to meet graded goals based on participant values. The action plan will include target goals, when/how/where tasks will be performed, strategies to overcome barriers, and how goals map to participant values.

- f. All participants will be asked by the health coach during the baseline visit to provide additional contact information. This will be collected on a separate sheet and will be entered into the ACCESS database used by the team.
5. After the initial baseline phone coaching session:
  - a. All i-STAND participants will receive 9 follow-up phone calls (10 contacts total) from their health coach over 6 months. An optional activPAL wear for i-STAND participants will take place at the 6-week mark, after which their data will be reviewed on a subsequent coaching call.
  - 2022 BUDGET CUT UPDATE: As of March 31, 2022, we are no longer offering the optional 6-week wear as a part of our staff time adjustments
  - b. All Healthy Lifestyle Control Participants will receive 9 follow-up phone sessions after their initial baseline phone coaching session (10 contacts total). Each call will cover a topic from the workbook (see Table 4). Relevant content from the Healthy Living workbook will be briefly reviewed and goals will be set. Follow-up calls will check-in with prior calls. The calls will occur every 2-3 weeks over the first 6 months of the study.
  - c. All study participants will be sent an activPAL to wear, as well as a survey, at the mid-point (Month 3) and will participate in a 3-month measurement visit by phone with a research specialist, repeating the measurements and instructions from the baseline visit. If the participant has requested that scheduling visits/reminders of visits be done via email, this information will be sent via email from the RS. They will receive by mail a \$30 incentive for completing the 3-month visit. All participants will receive a reminder phone call from the RS to confirm receipt of the packet containing the activPAL and the survey. If the packet was not received, the RS will resend another packet. At the 3-month mark, health coaches will also collect satisfaction data from the i-STAND group on their use of the devices. This information will be collected over the phone and input into REDCap by the coaches, so as to avoid contaminating the survey data collected by the blinded research specialists, who will be managing the primary survey distribution and data collection.
  - d. All participants (i-STAND and Healthy Lifestyles control group) will participate in a 6-month phone-based measurement visit. If the participant has requested that scheduling visits/reminders of visits be done via email, this information will be sent via email from the RS. The same measurements and assessments will be taken as at baseline and 3-

months except a study satisfaction questionnaire will be included in the self-reported survey. All participants will receive a \$30 incentive for completing measurements at the 6 month phone visit. After completing the 6-month measurement visit, all i-STAND participants will be re-randomized to EITHER receive i-STAND booster sessions (5 additional phone contacts) or no further intervention for 6 months. The health coach will call each participant after they complete their 6 month measurements to inform them of their assignment.

**2022 BUDGET CUT UPDATE:** As of March 31, 2022, there will be no re-randomization at the 6-month timepoint for those in the i-STAND cohort. Their coaching will end after the 10 initial sessions.

- e.
    - We have amended Supplement B to request permission to use email to send the link for the survey (REDCap) to participants for whom we have email addresses and who have given us permission to contact them using email.
    - We will track those participants who receive a device from a third party vendor on the internal PHI Disclosure Tracking Form (<https://ghriweb01.ghc.org/disclosuretrack/seldisc1.aspx>)
  - f. For those re-randomized into the i-STAND group, 5 booster calls spread over 6 months (about every 6 weeks) will focus on maintaining improvements (or continuing to improve for those who have not met goals), action planning, problem-solving, preventing relapse, and continuing to use previously learned skills and tools.
  - g. Participants in the i-STAND booster arm will have the option to wear the activPAL for an interim week between measurement visits (i.e., at 9 months) and receive an additional feedback chart to help monitor progress towards goals.
  - h. Participants in the i-STAND booster arm will receive a supplemental survey at 9-month mark to gauge their use of the tools – the standing desk and the Fitness wrist-band.  
**2022 BUDGET CUT UPDATE:** As of March 31, 2022, and due to the removal of the re-randomization stage for the i-STAND cohort taking place at 6-months (bullet "f"), there will be no further boosters. At 9-months, there will be no optional 9-month activPAL wear (bullet "g") nor will there be a 9-month supplemental survey (bullet "h").
6. All participants (i-STAND and healthy living control group) will participate in a final, 12-month phone-based measurement visit. Prior to the visit they will be mailed an activPAL to wear for a week. The same measurements will be taken as at baseline, 3 and 6 months, including a survey. All participants will receive a \$30 incentive for completing measurements at the 12 month visit. i-STAND cohort participants will be allowed to keep their wrist bands and standing desks. Once again, at this phone visit, if participants inquire about their blood pressure, we will advise them to see their provider if they have questions or concerns.  
**2022 BUDGET CUT UPDATE:** As of March 31, 2022, neither the i-STAND cohort nor the control cohort will have a 12-month assessment. As such, there is no \$30

incentive for completing a 12-month visit. This will be explained in the informational letter sent to participants.

7. For those participants who miss their scheduled 3, 6 or 12 measurement visits, we will attempt to reach them by phone and then by mail, encourage their participation and completion of that timepoint.

**2022 BUDGET CUT UPDATE:** As of March 31, 2022, neither the i-STAND cohort nor the control cohort will have a 12-month assessment

8. Shortly after completing the active, 6-month phase of the study, participants will receive a call asking for their oral consent to an interview. After completing the full year in the study including the final, 12-month visit, they will receive a letter thanking them for their participation and inviting them to participate in a final exit interview in the coming months. The letter will provide an opt-out if they do not want to do an exit interview. If we do not hear from the participant, we will assume they are open to receiving an exit interview phone call.).

**2022 BUDGET CUT UPDATE:** As of March 31, 2022, we will no longer be conducting exit interviews at the 6-month timepoint. And, as neither the i-STAND cohort nor the control cohort will have a 12-month assessment there will be no exit interview after this timepoint either.

**Table 4. Healthy Lifestyle Topics**

1. Coping with the Pandemic
2. Insomnia and Sleep
3. Stress & Anxiety
4. Low Mood & Aging
5. Healthy Eating & Hydration
Healthy Bones & Osteoporosis
Arthritis & Healthy Joints
Bladder Control
Preventing Falls
Stress & Anxiety
Writing an Advance Directive
Immunizations & Screenings
Managing your Medicines
Chronic Pain
Emergency Food & Water Supplies
Goal Setting & Tracking Progress
Communicating with Physicians

## **PARTICIPANT COMPLETION**

### **ORIGINAL COHORT**

1. Participants who completed all in-person visits will receive a completion certificate and a

- \$40 bonus for completing all visits (\$180 total).
- a. Participants in both groups may receive the workbook from the condition they did not receive and a summary of their activPAL data at the end of the study if they are interested.
  2. Once study results are available, a summary document of study findings will be prepared and shared with all participants.

**REMOTE COHORT:**

1. Participants who completed all phone visits will receive a completion certificate and a \$30 bonus for completing all visits (\$150 total).

**2022 BUDGET CUT UPDATE:** As of March 31, 2022, there will no longer be a 12-month visit, so the the new total amount is \$120. We will continue to give a \$30 bonus for completing the other timepoints (Baseline, 3 and 6 months).

  - a. Participants in both groups may receive the workbook from the condition they did not receive and a summary of their activPAL data at the end of the study if they are interested.
2. Once study results are available, a summary document of study findings will be prepared and shared with all participants.

**ORIGINAL (in-person) COHORT**

Additional information about assessments and measurements at in-person visit (baseline, 6 and 12 months):

**Cardiometabolic biomarkers:** We will measure HbA1c. To measure HbA1c, we will obtain a capillary whole blood sample obtained by finger prick, collected in a toothpick-sized capillary tube, and analyzed immediately using the Siemens DCA Vantage Analyzer. It performs a CLIA-waived HbA1c test that is IFCC and NGSP-certified.

Potential incidental findings may include a discovery that the participant has Diabetes. If this is discovered, the physician on call will notify the research specialist who will advise the participant to meet with their primary care provider as soon as possible.

**Weight, Height, Waist.** Weight will be measured using a calibrated Seca Digital weight scale. Height will be measured using a calibrated Seca Digital Stadiometer. Waist circumference will be measured twice at the superior border of the iliac crest and the average of two measurements used.

**COVID-19 UPDATE:** remote weight measurement at 6 and 12-months (until normal business resumes) will be collected as available and depends on the participant having a scale at home. Waist circumference will be collected using a Medline brand paper measuring tape which will be sent ahead of time to participants along with instructions on how to take an accurate measurement.

**Blood Pressure:** We will measure blood pressure (systolic and diastolic) three times to ensure accurate results. BP will be measured using an OMRON Digital BP Monitor with Intellisense. Model HEM907XL. We will also advise participants to avoid caffeine, tobacco and exercise in the 30 minutes

prior to the visit to ensure accuracy. After consent and when scheduling the baseline visit, we will ask the participant for height and weight so we can plan to send them the right size cuff with their BP monitor.

**COVID-19 UPDATE:** Until we return to normal business, we will be mailing Omron 3-Series BP7100 monitors (along with cuff and instructions on use) from a third party vendor (pending oral consent from the participant). These were recommended as a good option for home monitoring by Co-I [name] who has an expertise in blood pressure. Study measurement of blood pressure using these devices will be conducted during a phone call with the study Measurement RS, allowing for verbal instructions and questions from participants about the proper use of the device.

**Demographics:** Age, sex, education, marital status, race/ethnicity, retirement status, and other pertinent demographics will be measured using self-reported items on the baseline survey. Some demographic variables will be used as covariates in analyses.

**Psychosocial and environmental measures:** We will measure self-efficacy based on modifying measures that were developed in youth and adults (since none exist for older adults) and habit formation which will be assessed using a modification of the Self-Report Habit Index (e.g., "sitting is something I do without thinking").

**COVID-19 UPDATE:** We have added new sections to the surveys with validated instruments to better assess participant psychosocial status in the current environment. This includes lower extremity items from the Late-Life Function and Disability Instrument (LLFDI) for physical function; Generalized Anxiety Disorder Assessment (GAD-2) and the Perceived Stress Scale (PSS) for stress/anxiety; and COVID-19 impact. As always, participants can choose not to answer questions on the survey that make them uncomfortable. This information will be used by the statistician to determine whether any of the COVID-19 related variables are moderators of the interventions.

**Physical function.** The Short Physical Performance Battery (SBBP) will objectively evaluate lower extremity function with tasks for balance, gait speed, and lower-extremity strength (chair rise). Gait speed significantly improved in our prior study. SPPB will also be a covariate as it is associated with sedentarism.

**COVID-19 UPDATE:** Until we resume normal business, we will only be able to measure the chair rise as part of a remote assessment. The study RS will provide instructions and guidance to the participant via phone in order to conduct this measure remotely.

**Other behavior changes.** We will explore other activPAL metrics including sit-to-stand transitions, standing time, and step counts (as a measure of total physical activity). The same data-processing techniques will be used for these outcomes as for activPAL-measured sitting time. Self-reported sedentary behaviors will be assessed with the Sedentary Behavior Questionnaire to understand what types of sedentary behaviors are amenable to change. This measure has acceptable test-retest reliability and convergent validity.

**Quality of life** will be measured with the PROMIS Global Quality of Life Scale The Patient Health Questionnaire-8 will assess depressive symptoms and levels improved in our pilot work.

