**In person:**

Written consent to participate in the study will be captured at the in-person Baseline visit. One or two in-person health coaching sessions (depending on cohort). At Baseline, 6, and 12-month in-person visits, measurement data will be obtained. These measurement data include HbA1c via capillary fingerstick blood sample; weight, waist and wrist circumference; blood pressure, physical function, collecting the inclinometer (activPAL), and self-reported survey data. The Research Specialist will provide a beverage and a snack after collecting the finger-stick blood sample. Participants will arrive at the KPWHR research clinic for the baseline measurement session after an overnight fast of 12 hours (if they are able to), and will meet with the research specialist. Participants will be informed that they are free to withdraw from the study at any time. The consent materials will comply with HIPAA standards and will encourage participants to contact the principal investigator or project manager if they have additional questions.

In addition, we will collect adherence data (tracking completion of the in-person session and phone calls) for both intervention groups as well as additional inclinometer (activPAL) data from the i-STAND intervention group. We will audio-record phone sessions to be used in monitoring treatment fidelity.

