COVID-19 UPDATE: We have created an Addendum to Consent oral script to offer participants the option to continue coaching past the protocol timepoint as dictated in the original consent form until they are able to complete their remote 6 or 12 month assessments (for those receiving the booster intervention). The majority of participants will only have 10 coaching sessions and a subsection of i-STAND cohort will receive booster sessions. This is to ensure that participants are still working on their study goals up until their outcome measures can be assessed. For those who have already completed a 10th call, the coach will reach out by phone and ask if they are interested in optional additional coaching. If the participant is interested, the coach will use the oral consent process. For those who have not yet had this 10th session and have one forthcoming, the coach will ask at the end of that call if they are interested in optional additional coaching and use the oral consent process.

COVID-19 UPDATE: We have created an Addendum to Consent oral script to offer participants the option of receiving a blood pressure monitor (to keep) which we will send by a third party vendor. The oral consent is to verify their permission to share their mailing address and name with a third party in order to mail the device. Participants can choose not to allow this, in which case we will not collect their blood pressure data in the remote measurement visit.

REMOTE (phone) COHORT

No addendum consents will be implemented at this time with any newly recruited participants into the Remote Cohort. The additional coaching option will not apply to this cohort and the consent to give their name/address to a third party is covered in the screening that occurs during recruitment by the survey research group.

2022 BUDGET CUT UPDATE:

As of March 31, 2022, and upon approval of this IRB submission (Package 58) we will be mailing an Informational Letter to participants in both cohorts advising them of the change to the study and providing them a phone number to call if they have concerns. These letters will be sent in lieu of a revised consent form. In the letter we will highlight:

- Removing the 12-month visit which means \$30 less than they originally thought they'd receive for participation
- There is no change to risk
- There will be no potential for additional coaching beyond 6-months (only offered to a subset of the participant population)

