requested that scheduling visits/reminders of visits be done via email, this information will be sent via email from the RS. The same measurements and assessments will be taken as at baseline except a study satisfaction questionnaire will be included in the self-reported survey. All participants will receive a \$40 incentive for completing measurements at the 6 month visit. For those participants who do not show up to their scheduled 6-month visit, we will attempt to reach them by phone and then by mail, encourage their participation and completion of this timepoint. At this in-person visit, if participants inquire about their blood values or blood pressure, we will share the information with them but without interpretation and advise them to see their provider if they have questions or concerns. After completing the 6-month measurement visit, all I-STAND participants will be re-randomized to EITHER receive i-STAND booster sessions (5 additional phone contacts) or no further intervention for 6 months. The health coach will call each participant after they complete their 6 month measurements to inform them of their assignment.

- COVID-19 UPDATE: We will be ordering and sending directly to individual participants from a third party vendor (pending oral consent from participants) Omron BP Monitors (The Omron 3-Series BP7100 model) for any 6 and 12-month measurements. Participants will not be expected to return this device. Instructions will be included in the mailed packet that also includes the survey, activPAL, paper measuring tape (Medline 72" paper measuring tape). RS staff will call participants to conduct the chair-sit measurement and to verbally collect the BP/weight/waist measurements from participants. As usual, study packets mailed to participants will include return envelopes for the activPALs and the surveys.
- We will send incentives to participants when business returns to normal and we are able to send cash incentives. Participants will be notified that they will receive their incentives at a later time.
- We have amended Supplement B to request permission to use email to send the link for the survey (REDCap) to participants for whom we have email addresses and who have given us permission to contact them using email.
- We will track those participants who receive a device from a third party vendor on the internal PHI Disclosure Tracking Form (<https://ghriweb01.ghc.org/disclosuretrack/seldisc1.aspx>)

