**Aim 1: Determine the efficacy of i-STAND to improve primary and secondary outcomes at 6 months.**

*Primary Outcome Analysis:* Our primary outcomes are change from baseline in mean daily sitting time and systolic and diastolic blood pressure (described in Section C12). We will compare group means for our primary outcomes between participants randomized to i-STAND versus attention control using linear regression with generalized estimating equations (GEEs) including both outcome time points at 3 and 6 months. GEE is used to account for multiple outcomes measured on the same study participant along with relaxing the normality assumption that standard linear regression methods require. We will adjust for baseline covariates including participant age, sex, physical function, and respective baseline outcomes with other covariates that are imbalanced in preliminary analyses. If dropout is above 15%, we will employ imputation techniques to address missing data issues. However, our focus will be on minimizing dropout rates. Analyses for secondary outcomes including lipids, fasting glucose, weight, and waist circumference will be similar, adjusting for respective baseline outcomes in the analysis. *Aim 2: Determine the maintenance of sitting and blood pressure reductions over 12 months.* We will conduct a sequential series of analyses using a similar statistical framework as outlined for Aim 1, but using 12-month follow-up data. We will first run a regression model with three groups (attention control, i-STAND no boosters, and i-STAND with boosters) including baseline covariates as outlined above. We will then

assess differences in primary outcomes at 12 months in the two i-STAND groups: with and without the booster intervention. If a significant difference in a given primary outcome is found in sitting time at 12 months between the i-STAND booster versus no booster groups (Scenario 1), we will further compare the i-STAND booster and no booster groups to the attention control group. Scenario 1 assessments will determine if i-STAND with boosters is better than i-STAND without boosters and if either or both I-STAND groups are better than attention control at 12 months.

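### Some Original-cohort blood pressure changes subtract a clinic reading from a home reading on another device, and the primary model has no term for the switch

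*Combined protocol and SAP*

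**What the plan says.** Section 5.a (Aim 1) states: "Our primary outcomes are change from baseline in mean daily sitting time and systolic and diastolic blood pressure". The outcomes table in section 5 gives baseline to 6 months as the window for blood pressure.

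Three kinds of change feed this outcome:

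- **Clinic-clinic.** Original cohort, 6-month visit before the closure. Section 5, Original-cohort measurements: "BP will be measured using an OMRON Digital BP Monitor with Intellisense. Model HEM907XL".
- **Clinic-home.** Original cohort, 6-month visit after the closure. Baseline is as above. For follow-up, the COVID-19 update to the same measurement section says "Until we return to normal business, we will be mailing Omron 3-Series BP7100 monitors". Section 5, Original cohort, step 3d, likewise provides "Omron BP Monitors (The Omron 3-Series BP7100 model) for any 6 and 12-month measurements", taken by the participant while on the phone with the measurement specialist.
- **Home-home.** Remote cohort. The BP7100 is used at home at every visit.

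An Original participant may refuse to have name and address passed to the vendor, "in which case we will not collect their blood pressure data in the remote measurement visit" (section 4.o).

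Weight, a secondary outcome, moves from a calibrated clinic scale to a remote value that "depends on the participant having a scale at home".

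On adjustment, section 5.a says: "We will adjust for baseline covariates including participant age, sex, physical function, and respective baseline outcomes". The sentence goes on to include other covariates found imbalanced in preliminary analyses. Cohort, device and visit mode are not named, and none is a randomisation stratum. The same section promises secondary analyses for COVID-19 changes but does not describe them.

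**The concern.** For a clinic-home participant, change from baseline equals true change plus the home-minus-clinic difference in device, setting and operator. The primary model gives these participants the same intercept and baseline slope as everyone measured on one device throughout. If the two ways of measuring differ on average, the difference enters as extra spread in the outcome and as noise in the arm comparison whenever switched participants are unevenly split by chance. A slope fitted mainly to same-device pairs may also be wrong for switched pairs, which weakens the baseline adjustment.

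The visit schedule adds to this. The model uses 3- and 6-month outcomes, but Original participants receive only an activPAL and a survey at 3 months, while Remote participants repeat all measurements. Three-month blood pressure is therefore all home-device and 6-month blood pressure is a mixture, so time and device are partly entangled.

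At stake is avoidable loss of precision in two primary outcomes, and a free choice after the data are seen among possible COVID-19 adjustments.

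**Working it through.** **Inputs from section 5.a, power calculations.** 284 randomised 1:1, 15% loss, 241 analysed (120.5 per arm); pooled t-test; systolic 6.2 mmHg with SD of change 14.7; diastolic 4.0 mmHg with SD 9.5. Alpha is not stated; two-sided 0.05 is assumed.

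**Plan's own figure.** Noncentrality = d / (SD × √(2/n)).

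- Systolic: 6.2 / (14.7 × √(2/120.5)) = 3.27, power 0.903.
- Diastolic: 4.0 / (9.5 × √(2/120.5)) = 3.27, power 0.902.

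The stated 90% reproduces.

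**Assumed inputs.** The documents give neither the share switched, q, nor the mean home-minus-clinic shift, m. The ranges used are q = 10% or 20% and m = 5 or 10 mmHg, with the same m for diastolic.

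**Formulas, no pathway term.** SD of change = √(SD² + q(1−q)m²). SD of the error in the arm difference from chance imbalance = m × √(2q(1−q)/120.5).

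| q | m | Added variance | Systolic SD | Systolic power | Diastolic SD | Diastolic power | Imbalance SD (mmHg) |
|---|---|---|---|---|---|---|---|
| 10% | 5 | 2.25 | 14.78 | 0.90 | 9.62 | 0.90 | 0.19 |
| 10% | 10 | 9.00 | 15.00 | 0.89 | 9.96 | 0.87 | 0.39 |
| 20% | 5 | 4.00 | 14.84 | 0.90 | 9.71 | 0.89 | 0.26 |
| 20% | 10 | 16.00 | 15.23 | 0.88 | 10.31 | 0.85 | 0.52 |

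The imbalance SD is part of the variance already counted in the power columns, not an additional loss.

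**What a pathway term recovers.** It removes q(1−q)m². If the shift also varies between people with SD s, a further q·s² remains. With q = 20%, m = 10 and an assumed s = 8, systolic variance without the term is 216.09 + 16 + 12.8 = 244.89 (SD 15.65, power 0.865). With the term it is 216.09 + 12.8 = 228.89 (SD 15.13, power about 0.89), still below 0.903.

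**Bias if the shift differs by arm.** Bias = q × difference in shift. For differences of 2 to 5 mmHg, this runs from 0.10 × 2 = 0.2 to 0.20 × 5 = 1.0 mmHg. Nothing in the documents indicates such a difference.

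**The case against.** The strongest reply is that the plan is not silent and that little is lost. The imbalance rule in section 5.a could admit cohort, which is fixed at enrolment, if the arms differed on it. COVID-19 secondary analyses are promised. Allocation is 1:1 and the closure affected both arms. Readings are phone-guided, not unsupervised. Fasting is a weak part of the contrast, since it is asked for at baseline "after an overnight fast of 12 hours (if they are able to" and may also differ within clinic-clinic pairs. Section 5.a gives no source for the systolic SD of 14.7, and its power uses an unadjusted t-test while the planned model adjusts for baseline, so the powers above are indicative only.

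Most of this stands and keeps the point modest. It does not remove it. The imbalance rule acts only on baseline factors that differ by arm, so it would neither take out the added variance when the arms are balanced nor separate clinic-clinic from clinic-home pairs. The secondary analyses, whatever they turn out to be, leave the primary estimate as it is.

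Two stronger readings are not supported:

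- *The treatment comparison is biased.* A shift common to both arms cancels in expectation. Bias needs a shift, or a refusal rate for the monitor, that differs by arm, and no evidence of either is given.
- *All 100 Original participants switched, about 35% of 284.* Booster assignment follows the 6-month visit (section 5, step 3d). Yet the COVID-19 updates already refer to booster recipients awaiting 12-month assessments (section 4.o) and suspend the 9-month booster wear (step 3f). Some Original participants had therefore passed 6 months before the closure.

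**Conclusion.** The point holds as a precision and pre-specification issue. The switch is documented for Original participants with a post-closure 6-month visit, and the primary model does not account for it. Assuming 10-20% switched and a uniform mean shift of 5-10 mmHg, systolic power at 6.2 mmHg falls from about 90% to 88-90%. Diastolic power at 4.0 mmHg falls to 85-90% if its shift is as large. Person-to-person variation in the shift would lower these further, and a pathway term would not recover that part. The switch itself is certain from the text; its size rests wholly on the assumed ranges. Within-arm mean changes are distorted by any common shift even though the between-arm difference is not, in expectation. Worth correcting because the remedy is cheap, not because the trial's conclusion is in doubt.

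**What to change.** 1. In the primary systolic and diastolic models and in the weight model, add a three-level measurement-pathway factor: clinic-clinic, clinic-home, home-home. Define it by cohort and by whether the scheduled 6-month date, counted from randomisation, fell before or after a closure date stated in the SAP. Defined this way, it does not depend on post-randomisation behaviour. Let the baseline-value slope differ by pathway.
2. Pre-specify one sensitivity analysis restricted to participants measured on the same device at baseline and 6 months, and state that it selects on actual visit mode.
3. Report, per arm, the number switched and the number with no 6-month blood pressure reading.
4. Optionally, where imputation is used and a record value near 6 months exists, use the blood pressure already drawn from health records as an auxiliary variable for those without a reading.

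The cost is SAP wording, about four degrees of freedom (two for the factor, two for the slopes) among roughly 241 analysed participants, and one extra table. No new data are needed. The SAP should say that the term removes the mean shift only, and that scheduled date may misclassify a few visits near the closure.
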